### **9.5.3 Definition of Baseline Measurements**

Baseline measurements are those taken prior to the start of study drug administration.

#### 9.5.4 Methods for the Analysis of Device Dispense Failure Rate

For the analysis of the device dispense failure rate, a point estimate of the device dispense failure rate and its 90% confidence interval based on the exact binomial test will be constructed. Patients from all study centers will be pooled for the descriptive summary of these efficacy data by sex group.

#### 9.5.5 Pooling of Investigators

The data from all study centers will be pooled for the analysis of efficacy data.

#### 9.5.6 Methods for the Analysis of Categorical Efficacy Variables

For the analysis of the dichotomous outcome data, a point estimate and its 90% confidence interval based on the exact binomial test will be constructed. Patients from all study centers will be pooled for the descriptive summary of the efficacy data by sex group.

#### 9.5.7 Methods for the Analysis of Continuous Efficacy Variables

The method used to derive the efficacy endpoint time-weighted summed pain intensity difference (SPID) over the study period is described in this section. Pain intensity will be measured using an 11-point NRS with 0 (no pain) and 10 (worst possible pain).

Patients will provide the pain intensity (PI) and pain relief (PR) measures at baseline and at each evaluation time point after the initiation of the first on-demand dose of study drug:  $\frac{1}{4}$  [15 min],  $\frac{1}{2}$  [30 min],  $\frac{3}{4}$  [45 min], 1, 2, 4, 6, 8, 10, and 12 hours, then every 4 hours at 16, 20, 24, 28, 32, 36, 40, 44, 48, 52, 56, 60, 64, 68, and 72 hours.

The PID at each evaluation time point after the initiation of the first dose is the difference in pain intensity at the specific evaluation time point and baseline pain intensity [PID (evaluation time after the first dose) = pain intensity (baseline) – pain intensity (evaluation time after the first dose)]. The time-weighted SPID24 is the time-weighted summed PID over the 24-hour study period.

$$\text{Time-weighted SPID}_{24} = \sum [T(i) - T(i-1)] \times \text{PID}(i),$$

Where : T(0) = Time 0 (baseline), T(i) is the scheduled or unscheduled assessment time, and PID(i) is the PID score at time i for i=0 to 24 hours

Other time-weighted SPID, SPID48 and SPID72 will be derived similarly. TOTPAR over follow-up evaluation time periods (e.g., TOTPAR24, TOTPAR48, and TOTPAR72, etc.) will be derived from the PR data collected during the study using similar formula described above.

For the analysis of the continuous efficacy data, a point estimate and its 90% confidence interval will be constructed. Patients from all study centers will be pooled for the descriptive summary of the efficacy data by sex group

## **9.6 Analysis of Safety Data**

All patients who received at least one dose of study drug will be included in the summaries of safety data. An AE thesaurus, the Medical Dictionary for Regulatory Activities (MedDRA) will be used to map each AE verbatim term to lowest level term, preferred term, and System Organ Class for summary purposes. Adverse events occurring while patients are on study drug until 12 hours after the last dose will be summarized. Other safety data, such as premature terminations, vital signs (blood pressure, heart rate, and respiratory rate), oxygen saturation, and the use of concomitant medications will be tabulated.

Vital signs taken at baseline and follow-up time points will be summarized. Patients who had baseline data and at least one follow-up data will be included in the summary of vital signs by sex group. The descriptive summary statistics will be presented. A paired t-test will be used for the test of mean change from baseline to follow-up time points within each group.

## **10 STUDY MANAGEMENT**

### **10.1 Regulatory and Ethical Considerations**

#### **10.1.1 Regulatory Guidelines**

The Investigator agrees to conduct the study in accordance with the protocol, ICH guidelines on Good Clinical Practice (GCP), and national, state, and local laws of the pertinent regulatory authorities.

#### **10.1.2 Institutional Review Board**

The protocol, informed consent form (ICF), investigator's brochure, patient information, recruiting materials, subject compensation program (if any) must be approved in writing by an Institutional Review Board (IRB) before the study can be initiated at a site.

If the protocol is amended, AcclRx or the Investigator must obtain IRB for approval prior to implementation of the amendment. The Investigator must report promptly to the IRB all changes in the research activity and all unanticipated problems involving risk to human subjects or others, including all SAEs that have resulted in an expedited safety reporting.

The Investigator is responsible for obtaining continued review of the clinical study as specified by the IRB but at least annually.

#### **10.1.3 Informed Consent**

Each patient must provide written informed consent before any study-related procedures are started. It is the responsibility of the Investigator or designated staff member(s) to give a copy of the ICF to each potential patient and to be available to answer any questions the patient may have about the nature of the study and his or her participation in it. The individual responsible for explaining the consent form to the patient must witness the patient's signature on the form. It is the responsibility of the Investigator to

provide a copy of the IRB-approved consent form to the Sponsor (or designee) prior to the start of the study. If a protocol amendment substantially alters a study design or increases the potential risk to the patient, the consent form must be revised and submitted to the IRB(s) for review and approval prior to implementation. The revised consent must be used to obtain consent from patients currently in the study if they are affected by the amendment and from new patients prior to their enrollment in the study.

All enrolling patients are required to sign an IRB-approved Health Insurance Portability and Accountability Act of 1996 (HIPAA) authorization document.

#### **10.1.4 Study Documentation**

The protocol and any amendments signed and dated by the investigator, the completed financial disclosure form, and signed and dated statement of the investigator (e.g. Form FDA 1572), if applicable, and all other essential documents specified by ICH GCP will be provided to AcelRx or designee prior to initiation of the study at the investigational center.

Adequate source documentation will be maintained by the investigator and may be recorded on paper or directly into an electronic system. At a minimum this documentation will verify subject identification, eligibility, proper informed consent, visit dates, adherence to study procedures, reporting of safety and efficacy parameters, study drug dispensing, and study completion.

Source data may be recorded on paper or directly into an electronic system. A list of data directly entered into an electronic data capture system will be maintained.

Data should be entered into the CRF within 3 days of a patient completing the study. Queries should be resolved within 5 days of being issued.

#### **10.2 Withdrawals**

Individual patients might voluntarily drop from the study without completing all assessments. In such cases, the Investigator will document the specific reason for the incomplete information (e.g., withdrawal of consent) on the appropriate page of the CRF.

#### **10.3 Study Or Study Site Termination**

AcelRx may suspend or stop the study at all centers or at specific study centers due to (but are not limited to) the discovery of an unexpected, serious, or unacceptable risk to the patients enrolled in the study, a decision on the part of AcelRx to suspend or discontinue development of the product, failure of the Investigator to enroll patients into the study at an acceptable rate, failure of the Investigator to comply with regulatory authority or ICH Guidelines, or submission of knowingly false information.

#### **10.4 Study Monitoring**

AcelRx or designee will assign monitors who will perform on site monitoring as frequently as necessary and in accordance with ICH GCP.

Source documents and CRFs will be reviewed at monitoring visits and any findings will be discussed with the investigational staff. AcelRx expects that at monitoring visits study documents and staff will be available and a suitable space will be provided for review of the study documents. The monitor will meet with the investigator on a regular basis to provide feedback on the conduct of the study.

### **10.5 Data Quality Assurance**

Study auditing, data entry, verification and validation, and subsequent analysis will be performed by AcelRx, or its designees, in accordance with GCPs and established Standard Operating Procedures.

### **10.6 Access to Records**

The study may be subject to audit by AcelRx, its designee, or by regulatory authorities. If such an audit occurs, the Investigator must agree to allow access to required patient records. The Investigator should notify AcelRx promptly of regulatory authority audits that are scheduled, and must forward copies of any findings or audit reports to AcelRx promptly.

By signing this protocol, the Investigator grants permission to personnel from AcelRx, its representatives, and appropriate regulatory authorities for on-site monitoring and review of all appropriate study documentation, as well as on-site review of the procedures employed in data collection, where clinically appropriate.

### **10.7 Retention of Records**

The Investigator must arrange for retention of study records at the site for 2 years after the last approval of a marketing application in an ICH region and until there are no pending or contemplated marketing applications in an ICH region, or at least 2 years have elapsed since the formal discontinuation of clinical development of the investigational product. These documents should be retained for a longer period, however, if required by the applicable regulatory requirements or by agreement with AcelRx. It is the responsibility of AcelRx to inform the Investigator/Institution as to when these documents no longer need to be retained. The Investigator should take measures to prevent any accidental or premature destruction of these documents.

## **11 Publications**

All information related to this study is considered confidential information belonging to AcelRx. Data on the use of the study drug and results of all clinical and laboratory studies are considered private and confidential. None of the details, results, or other information for this study shall be published or made known to a third party without written consent from AcelRx, except for disclosure to regulatory agencies if required by law.

## APPENDIX I

### American Society of Anesthesiologists Physical Status Classification System

- I** Normal healthy patient
- II** Patient with mild systemic disease; no functional limitation—eg, smoker with well-controlled hypertension
- III** Patient with severe systemic disease; definite functional impairment—eg, diabetes and angina with relatively stable disease, but requiring therapy
- IV** Patient with severe systemic disease that is a constant threat to life—eg, diabetes and angina and congestive heart failure; patients with dyspnea on mild exertion and chest pain
- V** Unstable moribund patient who is not expected to survive 24 hours with or without the operation
- VI** Brain-dead patient whose organs are removed for donation to another
- E** Emergency operation of any type, which is added to any of the above six categories, as in ASA II E

## APPENDIX II

### DSM-IV Criteria for Substance Dependence

A maladaptive pattern of substance use leading to clinically significant impairment or distress, as manifested by three (or more) of the following, occurring at any time in the same twelve-month period:

1. tolerance, as defined by either of the following:
  - a. a need for markedly increased amounts of the substance to achieve intoxication or desired effect
  - b. markedly diminished effect with continued use of the same amount of the substance
2. withdrawal, as manifested by either of the following:
  - a. the characteristic withdrawal syndrome for the substance (see specific withdrawal syndromes in the DSM-IV)
  - b. the same substance (or closely related) substance is taken to relieve or avoid withdrawal symptoms
3. the substance is often taken in larger amounts or over a longer period than was intended
4. there is a persistent desire or unsuccessful efforts to cut down or control substance use
5. a great deal of time is spent in activities necessary to get the substance, use the substance, or recover from its effects
6. important social, occupational, or recreational activities are given up or reduced because of substance use
7. the substance is continued despite knowledge of having a persistent or recurrent physical or psychological problem that is likely to have been caused or exacerbated by the substance

NOTE: In an individual who denies dependence, substance dependence is assumed if there is evidence of a mental or physical disorder or condition that is usually a complication of prolonged substance use, e.g., DTs, cirrhosis, alcoholic neuropathy, esophageal varices from alcohol use, needle marks or abscesses from substance use.

\*Based on Diagnostic and Statistical Manual of Mental Disorders, Fourth Edition (DSM-IV Criteria for Substance Dependence)

## APPENDIX II (continued)

### DSM-IV Criteria for Substance Abuse

A maladaptive pattern of substance use leading to clinically significant impairment or distress, as manifested by one (or more) of the following, occurring at any time in the same 12-month period:

- (1) recurrent substance use resulting in a failure to fulfill major role obligations at work, school, or home (e.g., repeated absences or poor work performance related to substance use; substance related absences, suspensions, or expulsions from school; neglect of children or household)
- (2) recurrent substance use in situations in which it is physically hazardous (e.g., driving an automobile or operating a machine when impaired by substance-related disorderly conduct)
- (3) recurrent substance-related legal problems (e.g., arrests for substance-related disorderly conduct)
- (4) continued substance use despite having persistent or recurrent social or interpersonal problems caused or exacerbated by the effects of the substance (e.g., arguments with spouse about consequences of intoxication, physical fights)

**NOTE:** If a subject does not meet any of the above criteria, alcohol abuse will be assumed if the patient is consistently drinking more than 28 units of alcoholic beverages per week or female subjects who drink more than 21 units per week. 1 unit is defined as ½ pint of beer, 1 glass of wine or 1 measure of spirits.

\* Based on Diagnostic and Statistical manual of Mental Disorders, Fourth Edition (DSM-IV Criteria for Substance Abuse)

**APPENDIX III**  
**Patient Global Assessment**

The following question will be answered by the patient 24 hours after the first on-demand dose:

*“Overall, how would you rate the method of pain control during the last 24 hours?”*

The following question will be answered by the patient 48 hours after the first on-demand dose:

*“Overall, how would you rate the method of pain control during the last 48 hours?”*

The following question will be answered by the patient 72 hours after the first on-demand dose:

*“Overall, how would you rate the method of pain control during the last 72 hours?”*

- Poor (1)
- Fair (2)
- Good (3)
- Excellent (4)

**Healthcare Professional Global Assessment**

The following question will be answered by the HP 24 hours after the first on-demand dose:

*“Overall, how would you rate the method of pain control during the last 24 hours?”*

The following question will be answered by the HP 48 hours after the first on-demand dose:

*“Overall, how would you rate the method of pain control during the last 48 hours?”*

The following question will be answered by the HP 72 hours after the first on-demand dose:

*“Overall, how would you rate the method of pain control during the last 72 hours?”*

- Poor (1)
- Fair (2)
- Good (3)
- Excellent (4)

**APPENDIX IV**  
**Patient Usability Questionnaire**

How would you rate your experience with Zalviso regarding:

	Disagree	Somewhat Disagree	Somewhat Agree	Agree
I thought Zalviso was easy to use				
I had confidence in my ability to dose with Zalviso				
Zalviso consistently worked as I expected it to				
I did not understand how to use Zalviso				
I knew what to do if I dropped a tablet				
The use of Zalviso was not fully explained to me				
I would request to use Zalviso after my next surgery				

**APPENDIX V**  
**Nurse Usability Questionnaire**

How would you rate your experience with Zalviso regarding:

	Disagree	Somewhat Disagree	Somewhat Agree	Agree
I thought Zalviso was easy to set-up				
I had confidence in my ability to set-up Zalviso				
I did not spend much time having to trouble-shoot Zalviso during patient use				
Dropped tablets were disposed and accounted for appropriately and did not become a risk to the patient or others				
I found Zalviso time-consuming to set-up				
The Zalviso set-up instructions were not clear to me				
I would recommend Zalviso for the treatment of moderate to severe pain after surgery				

[figure not shown]

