
Trial Design: The study is a multicenter, open-label trial for 24 hours, and up to 72 hours, in patients 18 years and older who are undergoing surgery and are expected to require opioid analgesia for at least 24 hours. Patients who meet all inclusion and exclusion criteria at screening and following surgery will receive the Zalviso System.
 
Non-opioid analgesics may be used at any time along with the Zalviso System in a multimodal approach to the treatment of the patient’s postoperative pain. However, supplemental opioid medication (2 mg IV morphine) will only be allowed in the first 30 minutes after the first on-demand dose of study drug has been administered if necessary to keep a patient comfortable. Otherwise, supplemental opioid medication (2 mg IV morphine, no more frequently than hourly) is allowed only for pain due to ambulation or with the initiation of passive range of motion therapy throughout the remainder of the study. A pain intensity and pain relief score should be obtained prior to each administration of supplemental opioid medication.
 
Overall device performance and usability of the Zalviso System will be assessed by: proportion of patients with system-generated (device) errors and other failures of the device to function properly, number of patients with misplaced tablets (tablets inadvertently dispensed or dosed outside of the mouth), as well as the number of misplaced tablets, as assessed by study staff checks every 2 hours, and the Patient Usability Questionnaire (PUQ). Usability will also be assessed using the Nurse Usability Questionnaire (NUQ) which will be completed by study staff after they have experience with 5 or more patients or at the end of the study at the site.
	

Pain intensity will be self-recorded by the patient prior to first dose of study drug and then pain relief and pain intensity will be recorded by the patient at the following time points after the first on-demand dose of study drug:  $\frac{1}{4}$  [15 min],  $\frac{1}{2}$  [30 min],  $\frac{3}{4}$  [45 min], 1, 2, 4, 6, 8, 10, and 12 hours, then every 4 hours at 16, 20, 24, 28, 32, 36, 40, 44, 48, 52, 56, 60, 64, 68, and 72 hours. **During the study period, all PI, PR, and the patient global assessment (PGA) scores will be self-recorded by the patient in a source document provided by investigator's staff per the study schema.** The study staff must not record the patient's PI, PR, or global scores for the patient.

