G Each patient will complete an Usability Questionnaire at the end of his/her participation in the study and prior to completing the PGA; the study staff at each site will complete the Usability Questionnaire after he/she has completed 5 patients on the study or at the time the study is completed at the site.

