#### **6.1.4 End of Study**

Patients will be considered completers if they complete the study for a minimum of 24 hours. Patients who are withdrawn from the study for any reason prior to 24 hours will be considered early terminations.

At the time the patient discontinues from the study or a Drug Cartridge is changed, the number of tablets remaining in the Drug Cartridge as displayed on the Zalviso System display screen will be recorded in the source records.

The Patient Usability Questionnaire (Appendix IV) will be completed at the end of the study or at the time of early discontinuation. The Patient Usability Questionnaire will be completed before the patient completes the PGA (Appendix III).

Study staff will complete the Nurse Usability Questionnaire (Appendix V) when they have interacted with 5 patients, or when enrollment is completed at the study site. The study staff will download the controller data after its use by each patient using the data transfer cable and download utility software provided by AcelRx. The data files will then be transferred per AcelRx instructions.

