## **9 STATISTICAL METHODS AND DATA ANALYSIS**

### **9.1 Determination of Sample Size**

This is a multicenter, open-label, single treatment clinical study designed to evaluate the overall functionality of the Zalviso System (sufentanil sublingual tablet system) 15 mcg for the treatment of acute moderate-to-severe postoperative pain. A sample size of approximately 330 patients is planned for this study in order to have at least 315 patients receive study drug and have available efficacy data for data analysis.

A sample size of 315 patients will have 90% power to demonstrate that the device dispense failure rate is non-inferior to a target of 2%. This failure rate is the proportion of patients who experienced at least one of following events: (1) a system-generated error, (2) a tablet dispensed but not requested, or (3) a tablet dispensed when the Zalviso System is in lockout. All events listed above will be obtained from the Controller patient usage data.

This is based on the criteria that the upper limit of a 90% confidence interval (CI) of the device dispense failure rate is not worse than 5%. This calculation is based on the exact binomial test of one-sample proportion for a one-sided case against a 2% target proportion with a delta of 3%, and a one-sided significance level of  $\alpha=0.05$ . This sample size was generated from the SAS procedure PROC POWER for one-sample proportion. Exact power computations are based on the binomial distribution and computing formulas provided by Johnson and Kotz (1970). Assuming a 5% non-evaluable rate, a sample size of 330 patients is planned for this study.

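### Minor: the nurse questionnaire's dropped-tablet item has no 'did not occur' answer, so agreement mixes safe handling with no event seen

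*Protocol*

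**What the plan says.** Protocol section 2 lists nurse usability and satisfaction as an objective. Misplaced tablets and drug accountability form a separate objective.

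Protocol Appendix V contains the NUQ, which has seven statements. One reads "Dropped tablets were disposed and accounted for appropriately and did not become a risk to the patient or others". The answer columns are *Disagree*, "Somewhat Disagree", *Somewhat Agree* and *Agree*. There is no column for an event that did not occur. Another statement on the form reads "I did not spend much time having to trouble-shoot Zalviso during patient use".

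The protocol says in three places when staff complete the form:

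- Synopsis, Trial Design: "after they have experience with 5 or more patients or at the end of the study at the site".
- Study schema, footnote G: "after he/she has completed 5 patients on the study or at the time the study is completed at the site".
- Section 6.1.4: "when they have interacted with 5 patients, or when enrollment is completed at the study site".

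SAP 2.10.1 lists the NUQ as item (22) and says nothing more about it. The missing-data rules in SAP 2.10.2 cover pain intensity and pain relief only. Protocol section 6.2 states that neither usability questionnaire is validated.

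**The concern.** The dropped-tablet statement takes it as given that tablets were dropped. A nurse who saw none has no true answer on the form and can leave it blank, guess, or tick *Agree* because nothing went wrong. A blank has no handling rule. A tick is counted with the answers of nurses who did deal with a dropped tablet, because no tabulation by experience is planned.

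At stake is how one line of the usability results is read. The tablets are a Schedule II opioid, and a high proportion agreeing could be taken as nurses' testimony that dropped tablets were well controlled, when part of it reflects that none were seen. The sponsor's patient form avoids the problem: its dropped-tablet item in Appendix IV asks about knowing how to respond, which a patient who dropped nothing can still answer.

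**Working it through.** **What rate the plan gives.** The only planning rate for device events is the 2% target with a 5% limit in Protocol section 9.1 and SAP 2.1. Its power statement reproduces. With n = 315, an exact one-sided binomial test of 5% at α = 0.05 rejects at 9 or fewer failures. The exact size is 0.0449, and power at a true 2% is 0.896 against the stated 90%. The Clopper-Pearson upper limit at 9/315 is 4.93%, so the rule agrees with the confidence interval criterion.

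That 2% is defined by three Controller events: a system-generated error, an unrequested tablet, or a tablet dispensed in lockout. Misplaced tablets are not among them. Item (6) of the efficacy list does apply the label of dispense failure to a composite with misplaced tablets, but neither document attaches the 2% to that composite. No dropped- or misplaced-tablet rate is given anywhere, so a range has to be assumed.

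**Formula.** Let p be the assumed proportion of patients with at least one dropped tablet. If patients are independent and the nurse has full sight of each, then

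P(nurse has seen none in k patients) = (1 − p)^k.

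**Results for k = 5.**

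| Assumed p | (1 − p)^5 |
|---|---|
| 1% | 95.1% |
| 5% | 77.4% |
| 10% | 59.0% |
| 15% | 44.4% |
| 20% | 32.8% |

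The no-event share is one half at p = 1 − 0.5^(1/5) = 12.9%. The form can also be completed at other counts. With 3 patients the halfway point is p = 20.6%, and with 10 patients it is 6.7%.

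**What this does to the item.** Let s be the no-event share and q the proportion of exposed nurses who would agree. If every unexposed nurse ticked *Agree*, the tabulated proportion would be s + (1 − s)q, which cannot fall below s whatever the exposed nurses report. At p = 5% that floor is 77.4%; at p = 20% it is 32.8%. This is a worst case, because the documents do not tell us how unexposed nurses would answer.

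**Direction of the assumptions.** Nurses on shifts see only part of each patient's 24 to 72 hours, which raises the no-event share. Completion beyond 5 patients, which the Synopsis wording allows, lowers it. Completion with fewer than 5, possible when enrollment or the study ends at a site, raises it.

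**Timing wording.** Interacting with 5 patients, having 5 patients complete, and having experience of 5 or more are different triggers. The fallback also differs: end of enrollment at the site in section 6.1.4, end of the study at the site in the other two places. Sites could follow any of them.

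**The case against.** The strongest reply is that the plan does not depend on this item for tablet control. Staff check for misplaced tablets every 2 hours and document each find (Protocol section 6.1.3). They record who found it, when and where (section 5.4), and the sponsor or its designee compares cartridge counts with site records and investigates discrepancies (section 5.5). Misplaced tablets have their own endpoints (SAP 2.10.1 items (4) to (6)). The NUQ is unvalidated and descriptive, with no hypothesis or threshold. All of this stands and is why the point is minor. It does not make the item interpretable, because nothing links those records to the nurse who fills in the form.

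The documents do not support several stronger readings that a reader might infer:

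- *The trouble-shooting item has the same fault.* It does not. It asks about time spent, so a nurse who met no problem can truthfully agree, and low burden is what the item measures. Restricting it to staff who had problems would bias it against the device.
- *About 90% of nurses will have seen nothing, because (1 − 0.02)^5 = 90.4%.* That uses a rate that excludes dropped tablets. It is not a trouble-shooting rate either, since retraining notifications and suspected failures without an error message also call for nurse action and have no stated rate.
- *Most nurses will be rating something they never saw.* At 5 patients this needs a rate below about 12.9% per patient, which the documents neither state nor rule out.
- *Nurses are forced to answer, or the item cannot measure anything.* No passage requires every item to be completed, and nurses who handled a dropped tablet can answer meaningfully.

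**Conclusion.** The point holds, at minor severity, for one item of seven. The dropped-tablet statement presupposes an event, has no answer for its absence, and would be tabulated without regard to exposure. The share of nurses affected at 5 patients is about 95% to 33% for an assumed 1% to 20% of patients with a dropped tablet, given independent patients and full sight of each. The rate is an assumption, but the defect does not depend on a majority being affected: at the top of that range about a third would still be rating an event they had not seen. The three completion times need to be made consistent. The wording differences show an inconsistency, not that any one time is wrong; asking later gains experience but risks recall problems and loss of staff. Sample size, power and the primary device failure analysis are unaffected.

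**What to change.** 1. In Appendix V, add a *Did not occur* answer to the dropped-tablet item only. Leave the trouble-shooting item unchanged.
2. Under SAP 2.10.1 item (22), state that this item is summarized among staff who saw a dropped tablet, with the number who did not shown separately.
3. Reconcile the completion time in the Synopsis, schema footnote G and section 6.1.4 into one rule with one fallback.

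The cost is one response box, one SAP sentence and one timing sentence. The downside is a smaller denominator for a single descriptive item; that denominator is the number of staff with experience to report.
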